10.2. Adverse Events (AEs)

All AE summaries will be restricted to treatment-emergent adverse events (TEAEs), which are defined as any AEs that newly appear, increase in frequency, or worsen in severity following initiation of study medication. If it cannot be determined whether the AE is treatment emergent due to a partial onset date, then it will be counted as treatment emergent. Verbatim terms on eCRFs will be mapped to preferred terms and system organ classes using MedDRA (version 17.1).

Summaries that are displayed by system organ class and preferred terms will be ordered by descending order of incidence for all OCA treated patients of system organ class and by preferred terms within each system organ class. Summaries of the following types will be presented by treatment group:

- Overall summary of TEAEs
- Subject incidence of TEAEs and the total number of entries by MedDRA system organ class and preferred term.
- Subject incidence of drug-related TEAEs by MedDRA system organ class and preferred term. Related AEs are those with relationships reported as “Definite,” “Probable,” “Possible,” or with a missing relationship.
- Subject incidence of serious adverse events (SAEs) by MedDRA system organ class and preferred term.
- Subject incidence of TEAEs leading to investigational product withdrawal or study discontinuation by MedDRA system organ class and preferred term. This is a subset of the AEs where Action Taken with Study Medication is checked as “Drug Withdrawn” or Subject Discontinued from Study is checked.
- Subject incidence of TEAEs leading to investigational product withdrawal by MedDRA system organ class and preferred term. This is a subset of the AEs where Action Taken with Study Medication is checked as “Drug Withdrawn”.
- Subject incidence of TEAEs leading to study discontinuation by MedDRA system organ class and preferred term. This is a subset of the AEs where Subject Discontinued from Study is checked.
- Subject incidence of TEAEs by MedDRA system organ class, preferred term, and maximum severity will be presented. At each level of subject summarization, a subject is classified according to the maximum severity if the subject reported one or more events. AEs with missing severity will be considered severe for this summary.
- Subject incidence of follow-up TEAEs and the total number of entries by MedDRA system organ class and preferred term. Follow-up TEAEs are defined as those TEAEs with onset after the Week 24 visit, for those subjects not continuing to the LTSE phase.

The summaries above will be repeated presenting only preferred term ordered by descending order of incidence for all OCA treated patients, excluding system organ class.

The incidence of pre-treatment AEs and pre-treatment SAEs occurring after ICF signoff and before the first dosing of investigational product (OCA or placebo) will be tabulated in the same manner as above for all subjects participating in the washout period.

The following listings will be presented by subject:

- All AEs
- Serious AEs (subset of the AEs where serious is marked as “Yes”)
- Death information will be provided in a separate listing, should any deaths occur
- Severe AEs (subset of AEs where severity is marked as “Severe” or severity is missing)
- Related AEs (subset of AEs where relationship to study medication is marked as “Definite”, “Possible” or “Probable”)
- AE’s leading to withdrawal of investigational product (subset of AEs where action taken with study medication is marked as “Drug Withdrawn”)
- AE’s leading to Study Discontinuation (subset of AEs where subject discontinued from study is checked)

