The dose-ranging aspect of the trial design targets doses known to be therapeutic for PBC (5 mg and 10 mg), another cholestatic liver disease, but also incorporates lower doses to 1) Allow identification of the minimally safe and effective dose, and 2) Further characterize the exposure-response relationship in this patient population. The nested dose-rising approach allows for a more robust characterization of the value of titration to address potential tolerability concerns and the exposure-response relationship by addressing intra-subject variability. The nested dose-rising approach also limits the needed number to treat which is important given the rarity of the disease and limited pool of patients from which to recruit, and minimizes the number of patients unnecessarily exposed to study medication.

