**6.4. Dose Adjustment Criteria and Dose Titration****6.4.1. Double-Blind Phase**

Following randomization, subjects will administer the assigned, blinded treatment once daily for 12 weeks.

After 12 weeks, the subject's dose will be titrated as follows, providing there are no limiting safety or tolerability concerns in the opinion of the Investigator, while maintaining the trial blind: the 1.5 mg OCA treatment group will titrate to 3 mg, the 5 mg OCA treatment group will titrate to 10 mg OCA, and the placebo group will remain on placebo. DB treatment will continue for a further 12 weeks at that dose.

Any subjects whose dose is not titrated, due to safety or tolerability concerns, will remain on their starting treatment (1.5 mg OCA, 5 mg OCA, or placebo) for the remainder of the DB phase to Week 24.

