6.2.7. Multiple Comparisons/Multiplicity

A hierarchical approach will be used for multiplicity adjustments. If the primary efficacy analysis is statistically significant ($p < 0.05$), the following order will be used in the testing procedure to compare the change from Baseline in ALP between OCA and placebo:

- Week 12: OCA 5 mg treatment group (randomized to 5 mg for the initial 12 weeks followed by 10 mg for the latter 12 weeks) vs. placebo
- Week 24: OCA 3 mg treatment group (randomized to 1.5 mg for the initial 12 weeks followed by 3 mg for the latter 12 weeks) vs. placebo
- Week 12: OCA 1.5 mg treatment group (randomized to 1.5 mg for the initial 12 weeks followed by 3 mg for the latter 12 weeks) vs. placebo

If at any step the comparison is not statistically significant, then all subsequent comparisons will be exploratory rather than confirmatory.

Multiplicity adjustments will not be applied for any other statistical testing.

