7.5. Safety Population

The Safety population will include all subjects who receive any amount of investigational product. Treatment assignment will be based on the treatment actually received. The Safety population will be used for the analysis of all safety data.

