10. SAFETY ANALYSES

All safety analyses will be based on the Safety Population. The evaluation of the effects of OCA on safety parameters in the PSC population is a primary objective of this study.

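### The planned adverse event incidence tables combine each arm's starting and titrated doses over 24 weeks; add tables by dose period and dose at onset.

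*SAP*

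**What the plan says.** **How AEs are tabulated.** SAP 10.2 states: "Summaries of the following types will be presented by treatment group". This governs the overall, drug-related, serious, withdrawal and maximum-severity summaries. The main TEAE table gives subject incidence plus the total number of entries. SAP 10.3 does the same for the two AEs of special interest, pruritus and dyslipidaemia.

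**What a treatment group is.** SAP 6.2.7 describes the upper-dose group as "randomized to 5 mg for the initial 12 weeks followed by 10 mg for the latter 12 weeks" and the lower-dose group as "randomized to 1.5 mg for the initial 12 weeks followed by 3 mg for the latter 12 weeks". Under Protocol 6.4.1, subjects who are not titrated "will remain on their starting treatment (1.5 mg OCA, 5 mg OCA, or placebo) for the remainder of the DB phase to Week 24". SAP 10.1.1 counts these subjects, but no AE table separates their events.

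**How subjects are assigned.** SAP 7.5, for the Safety population: "Treatment assignment will be based on the treatment actually received". It gives no rule for allocating events between the two doses of one arm.

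**The only split of post-dose AEs by time.** SAP 10.2: "Follow-up TEAEs are defined as those TEAEs with onset after the Week 24 visit". There is nothing at Week 12, and the AE tables listed in Appendix A add nothing.

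**What the trial wants to know.** SAP 10: "The evaluation of the effects of OCA on safety parameters in the PSC population is a primary objective of this study". Protocol 4.6.2 gives the overall goal as finding doses that work and are well tolerated, and says of the design: "The nested dose-rising approach allows for a more robust characterization of the value of titration to address potential tolerability concerns".

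**The concern.** ALP is tested separately at Week 12, when the arms are on 1.5 and 5 mg, and at Week 24, when they are meant to be on 3 and 10 mg. AE incidence has no matching split. One figure per arm covers the starting dose, the doubled dose and the subjects who were never titrated.

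Timing relative to titration is informative here by the protocol's own account. Protocol 4.5 expects dose-dependent worsening of pruritus and calls liver toxicity an important potential risk in PSC. Protocol 11.1.3.1 says that severe pruritus tends to appear within two weeks of starting therapy.

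At stake is whether the study report can set AE incidence beside the ALP result for each dose step. Without a prespecified table, any such split would be made after database lock and labelled post hoc.

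**Working it through.** The plan gives no figure for AEs: the sample size in SAP 4 is for ALP. The check is therefore to see what each planned output shows, and then what a pooled incidence can and cannot tell the reader.

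**Step 1: outputs side by side**

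| Data | Planned presentation | Separates pre- and post-titration? |
|---|---|---|
| TEAEs, related, serious, withdrawal, maximum severity (SAP 10.2) | By group over the whole double-blind phase | No |
| Pruritus AEs (SAP 10.3.1) | Incidence by group; Kaplan-Meier for first onset and first severe event, with numbers at risk; event days per patient-year | First onset and first severe event: largely. Recurrence and event days: no |
| Dyslipidaemia AEs (SAP 10.3.2) | Incidence by group; Kaplan-Meier for first onset | First onset: largely. Recurrence: no |
| Hepatobiliary and all other AEs | Incidence by group only | No |
| Laboratory values, vital signs (SAP 10.4, 10.5) | By visit: Weeks 2, 6, 12, then 14, 18, 24 | Yes |
| Pruritus VAS, 5-D, partial Mayo, CDAI (SAP 9.2.6) | Compared with placebo at Weeks 12 and 24 | Yes |

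**Step 2: what one pooled incidence hides**

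Let p1 be the first-onset risk in Weeks 0-12, and p2 the risk in Weeks 12-24 among those still event-free. Ignoring dropout, the 24-week incidence is

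P = 1 - (1 - p1)(1 - p2), so p2 = 1 - (1 - P)/(1 - p1).

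Take P = 10/25 = 40%, an assumed value:

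- p1 = 40%: p2 = 1 - 0.60/0.60 = 0%
- p1 = 22.5%: p2 = 1 - 0.60/0.775 = 22.6%
- p1 = 0%: p2 = 1 - 0.60/1.00 = 40%

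The planned incidence cell reads 10/25 in all three cases. In counts, 4/25 (16%) before titration and 6/21 (28.6%) of the remaining subjects after it also give 10/25.

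**Step 3: how much a split could show**

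Inputs from SAP 4: 25 per arm and 20% dropout, so 25 x (1 - 0.20) = 20 if all of the dropout has occurred. Exact (Clopper-Pearson) 95% intervals:

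| Events/subjects | 95% CI |
|---|---|
| 0/25 | 0-13.7% |
| 5/25 | 6.8-40.7% |
| 10/25 | 21.1-61.3% |
| 0/20 | 0-16.8% |
| 5/20 | 8.7-49.1% |
| 10/20 | 27.2-72.8% |

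At 25 per arm, power for an assumed difference between two arms within one period is 33% for 20% vs 40%, 70% for 10% vs 40%, and 85% for 20% vs 60%. Showing non-titrated subjects separately makes the 3 and 10 mg cells smaller still.

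**The case against.** The strongest reply is that much of the safety information is already readable by dose step, and that the rest can be recovered. Several readings that go further than the point made here do not survive it.

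- *Tolerability cannot be read by dose at all.* A reader might infer this, but the table in the working shows otherwise: patient-reported pruritus is compared with placebo at the same two timepoints as ALP.
- *The trial cannot attribute AEs to dose.* The documents do not support this. Onset dates are handled in SAP 6.3.3, and all AEs and all exposure data are listed by subject. What is missing is a planned summary.
- *Recurrences vanish.* They enter the total number of entries in the main TEAE table and the special-interest tables. They are just not placed before or after titration.
- *The pruritus split is lost.* The planned Kaplan-Meier curve would largely show a step after Week 12, with the number still at risk.
- *Assignment by treatment received is meaningless.* It can reasonably be read as the sequence received. It simply does not allocate events within a sequence.
- *The design exists to answer tolerability by dose.* The primary efficacy comparison is Week 24 ALP in the 10 mg group against placebo, and nothing is powered for AEs. Tolerability by dose is one of several stated aims.

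It is also fair to say that within an arm, dose is confounded with time, prior exposure, dropout and the investigator's decision to titrate. Even the Week 24 ALP analysis is by randomized sequence and includes non-titrated subjects.

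All of this stands and limits the point. It does not supply a planned AE summary by period for events other than pruritus and dyslipidaemia, nor a rule for recurrence or worsening after titration.

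**Conclusion.** The point holds in limited form. The planned AE incidence tables are by treatment sequence over the whole 24 weeks and do not show incidence separately for the starting doses (1.5 and 5 mg) and the titrated doses (3 and 10 mg), although tolerability by dose is a stated aim. The gap matters most for events with no planned timing analysis, hepatobiliary events in particular, and for assigning recurrence or worsening to a period.

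The size is a matter of information lost. One pooled 40% is compatible with all of the risk falling before titration, all of it after, or an even split. The 40% and the AE rates used for power are assumptions; only the 25 per arm and the 20% dropout come from the plan.

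A split would give one clean result, the randomized comparison of 1.5 mg and 5 mg with placebo over Weeks 0-12. Everything after titration would be descriptive. This is an omission from the table plan that should be put right; it does not undermine the trial.

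**What to change.** Add to SAP 10.2 and Appendix A:

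1. Tables of TEAEs, severe TEAEs, pruritus and TEAEs leading to discontinuation, by period (first dose to the Week 12 titration; titration to Week 24) and by actual dose at onset, with subject-years per period and placebo over the same period.
2. A rule that recurrence or worsening after titration is counted in the second period.
3. Non-titrated subjects shown separately in the second period.
4. A definition of the boundary that also works for placebo and non-titrated subjects, and of how partial onset dates fall around it. The visit date alone is not enough: under Protocol 8.6.7, subjects in PK sampling take the lower dose at the Week 12 visit and the titrated dose the next day.
5. A statement that Weeks 0-12 against placebo is the randomized comparison of the starting doses. Comparisons in Weeks 12-24 and within an arm should be footnoted as descriptive because of selection, confounding with time and small cells.

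The cost is a few extra tables from data already collected. Their intervals will be wide, and the footnotes are needed so that second-period differences are not read as dose effects. The change should be made before the double-blind database lock so that the tables count as planned.

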**Table 1: Schedule of Trial Procedures: Double-Blind Phase (Continued)**

Visit Type a	Screening (Day -30 to Day -1)	Day 0 b	Visit W2	Visit W6	Visit W12 c	Visit W14	Visit W18	Visit W24 d / LTSE D1/ EOT e	FU (4 wks) f
Visit Windowg	≤30d		±3d	±1wk	±1wk	±1wk	±1wk	±1wk	±1wk
Dispense Investigational Product		X q			X			X r	
Investigational Product Accountability/ Compliance s			X	X	X	X	X	X	
Laboratory Evaluationst									
Serum Chemistry, Hematology, & Coagulation Parameters	X u	X	X	X	X	X	X	X	X
FGF-19		X			X			X	
CRP		X			X			X	
ELF Markers & Other Analytes v		X			X			X	
Plasma Bile Acids		X			X			X	
C4		X			X			X	
PK w					X			X	
Apolipoprotein & NMR Lipoprotein Panel		X			X			X	
Dipstick Urinalysis	X	X			X			X	
Urine Pregnancy Test x	X	X			X			X	X
Fecal Sample y		X			X			X	
Genetics Study z		X						X	

- a Subjects must be fasted prior to all clinic visits (except Screening) and investigational product should not be administered prior to clinic visits (see [Section 8.1](#)).
- b Day 0 must occur by Day 31 for a subject to be eligible to continue in the trial.
- c Week 12 is the Dose Titration visit.
- d The Week 24 visit is the final visit during the DB treatment period. For subjects who continue into the LTSE, the Week 24 visit is also Day 1 of the LTSE, and unblinding occurs after the Week 24/LTSE Day 1 procedures have been completed (except dispensing of open-label investigational product).
- e End of treatment (EOT) visit is completed for any randomized subject who discontinues the study prior to reaching Week 24 of the DB phase; this should occur as close as possible to the final dose of investigational product. If a subject discontinues on the day of a scheduled trial visit, the procedures from the scheduled visit will be recorded as EOT in the CRF.
- f Follow-Up visit: If a subject discontinues the study prior to the end of Week 24 or does not proceed into the LTSE, he/she returns to the site for a Follow-Up visit, which should occur 4 weeks ( $\pm 1$  week) after her/his last dose of investigational product.
- g Timing of all visits is relative to Day 0.
- h Height is measured at the Screening visit only.

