#### **8.6.12. Follow-Up Visit: Double-Blind Phase**

Subjects who terminate participation in the trial prior to the Week 24 visit or complete the Week 24 visit but do not proceed to LTSE, should have a Follow-Up visit 4 weeks after their last dose of investigational product:

- Assess and record AEs.
- Record current concomitant medications.
- Record vital signs.
- For subjects with UC: obtain partial Mayo score (excluding endoscopy).
- For subjects with CD: complete CDAI assessments and assign CDAI score.
- Administer pruritus VAS subject questionnaire and 5-D Itch questionnaire.
- Obtain blood samples for serum chemistry, hematology, and coagulation.
- Perform a urine based  $\beta$ -hCG pregnancy test in females of childbearing potential. If the urine pregnancy test is positive it should be repeated as a serum pregnancy test.
- Record the visit in IWRS.

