#### **11.1.4. Reporting of Adverse Events and Serious Adverse Events**

##### **11.1.4.1. Reporting of Adverse Events**

AE data will be collected from the time that signed informed consent is obtained until the subject fully completes her/his trial participation of the trial.

All AEs, whether believed by the Investigator to be related or unrelated to the investigational product, must be documented in the subject’s medical records, in accordance with the Investigator’s normal clinical practice and on the AE CRF. Each AE is to be evaluated for duration, intensity, frequency, seriousness, outcome, other actions taken, and relationship to the investigational product.

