6.3.3. Partial Dates

If only a partial date is available and is required for a calculation, the following standards will be applied:

- Diagnosis date (eg, PSC diagnosis date)
 - For missing day only: Day will be imputed as the first day of the month (ie, 01).
 - For missing day and month: Day and month will be imputed as the first day of the year (ie, 01 January).
- Start dates (eg, AE onset date or start date of medication)

- For missing start day only: Day will be imputed as the first day of the month (ie, 01) with the following exception: if the partial date falls in the same month and year as the date being used in the calculation (eg, first dose date, informed consent date), then the partial date will be imputed to equal the date being used for the calculation.
- For missing start day and month: Day and month will be imputed as the first day of the year (ie, 01 January) with the following exception: if the partial date falls in the same year as the date being used in the calculation (eg, first dose date, informed consent date), then the partial date will be imputed to equal the date being used for the calculation.
- Imputed start dates must be prior to the stop date.
- Stop dates (eg, AE resolution date or stop date of medication)
 - For missing stop day only: Day will be imputed as the last day of the month (ie, 28, 29, 30, or 31).
 - For missing stop day and month: Day and month will be imputed as the last day of the year (ie, 31 December).
 - Imputed dates should not extend beyond the DB phase (ie, date of completion or discontinuation of the DB phase).
 - Imputed stop dates must be on or after the start date.

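### The SAP anchors follow-up TEAEs on the Week 24 visit, so subjects who stop early cannot enter the only summary of events that begin after treatment

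*SAP*

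**What the plan says.** SAP 10.2 defines TEAEs as "any AEs that newly appear, increase in frequency, or worsen in severity following initiation of study medication". The definition has a start and no end. Among the summaries by treatment group is one of follow-up TEAEs: "Follow-up TEAEs are defined as those TEAEs with onset after the Week 24 visit, for those subjects not continuing to the LTSE phase". The same section says its summaries will be repeated by preferred term alone.

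The protocol separates two kinds of last double-blind visit. Table 1, footnote e: "End of treatment (EOT) visit is completed for any randomized subject who discontinues the study prior to reaching Week 24 of the DB phase". Footnote f then gives the follow-up visit to two groups: "If a subject discontinues the study prior to the end of Week 24 or does not proceed into the LTSE". Section 8.6.12 repeats this. It names "Subjects who terminate participation in the trial prior to the Week 24 visit or complete the Week 24 visit but do not proceed" to the LTSE, says that they "should have a Follow-Up visit 4 weeks after their last dose of investigational product", and lists adverse event recording first among the procedures. Section 11.1.4.1 sets the collection period: "AE data will be collected from the time that signed informed consent is obtained until the subject fully completes her/his trial participation".

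**The concern.** The protocol collects adverse events after the last dose in early terminators and in Week 24 completers who decline the extension. The SAP's only category for events that begin after treatment depends on a visit that the first group does not have.

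Safety is a primary objective (SAP 2 and 10), and the missing group matters for it. Protocol 7.4.1 requires investigational product to stop after certain unexplained rises in transaminases or bilirubin. Section 7.4.2 calls for discontinuation when severe pruritus cannot be tolerated. Section 11.1.8 notes that drug-induced liver injury can appear or progress after the drug is stopped. A follow-up table limited to Week 24 completers who decline the extension leaves out the subjects in whom events after stopping are of most interest.

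**Working it through.** No figure in the plan depends on this definition, so there is nothing to reproduce. The check sets the SAP definition against the protocol's visit rules.

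**Step 1: each type of subject under the rules as written** (protocol Table 1 footnotes d to f, 8.6.10 to 8.6.12; SAP 10.2).

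| Subject | Last double-blind visit | Double-blind follow-up visit with AE recording | Week 24 visit to anchor on | Can have a follow-up TEAE | Events in overall TEAE tables |
|---|---|---|---|---|---|
| Completes Week 24, enters LTSE | Week 24 / LTSE Day 1 | No | Yes | No, excluded by design | Yes |
| Completes Week 24, declines LTSE | Week 24 | Yes | Yes | Yes | Yes |
| Stops before Week 24 | EOT | Yes | No | No | Yes |

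The third row is the gap. These subjects meet the condition of not continuing to the LTSE but cannot meet the condition of onset after a Week 24 visit.

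**Step 2: does any other summary separate these events?** SAP 10.2 has tables for events leading to drug withdrawal and to study discontinuation, but they select on the action taken and not on timing relative to the last dose. No other listed adverse event table splits events at the last dose.

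**Step 3: is the table in Appendix A?** The adverse event tables there run from 14.3.1.1 to 14.3.1.11.2. None is titled for follow-up TEAEs, either by system organ class or by preferred term.

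**Step 4: does the SAP use wording elsewhere that would cover early terminators?** Yes. The limit on imputed stop dates in SAP 6.3.3 refers to the "date of completion or discontinuation of the DB phase".

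**Step 5: size of the affected group.** Inputs are the 20% dropout in SAP 4 and protocol 12.2, 25 subjects per group, and 75 in total.

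- Per group: 0.20 × 25 = 5.
- Total: 0.20 × 75 = 15.
- Over an assumed dropout range of 5% to 30%: 0.05 × 75 = 3.75 and 0.30 × 75 = 22.5, so about 4 to 23 subjects.

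These are ceilings at each dropout rate. A subject who withdraws consent or is lost to follow-up may never attend the follow-up visit.

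**The case against.** **The visits may be the same.** Protocol Table 1 puts Week 24, LTSE Day 1 and EOT in one column, so a programmer might treat EOT as the Week 24 visit, and early terminators would then be included. This stands only as an ambiguity. Footnotes d and e keep the visits distinct, and the SAP gives no mapping rule. The mapping would also clash with SAP 8.1, which counts a subject as completing Week 24 if an ALP value exists at that visit: an early terminator with an EOT ALP would become a completer.

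**Nothing is lost.** This stands. Every adverse event is listed by subject and every TEAE enters the overall tables. For pruritus, SAP 10.3.1 plans time to resolution of the most severe event, with separate summaries for those who discontinue because of it. The gap is in one descriptive summary.

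**A stronger reading.** A reader might infer that early terminators' off-drug events are counted as on-treatment and inflate the counts in the arm that loses more subjects. The documents do not support this:

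- The SAP has no on-treatment adverse event category.
- Events after the last dose are in the overall tables because the TEAE definition has no end. The same holds for completers who decline the extension.
- SAP 10.1.1 ends exposure at the last dose, so follow-up time is not counted as time on drug.
- Follow-up TEAEs are a subset of TEAEs. Redefining them would remove nothing from the overall tables.
- Nothing in the documents gives an event rate or a direction from which inflation could be derived.

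**Conclusion.** The point holds as a gap in a stated definition. Read literally, SAP 10.2 shuts early terminators out of the follow-up TEAE summary although the protocol collects the relevant events, and Appendix A has no table for that summary. The result is an incomplete safety summary on a primary objective. It is neither data loss nor an inflated count.

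The importance is low. No efficacy result, no overall TEAE count and no exposure figure changes. The 15 of 75 subjects is an upper illustration that rests on the sample-size dropout assumption. It is not an estimate of how many subjects will have an omitted event. The conclusion assumes that Week 24 and EOT are separate visits, as the Table 1 footnotes state.

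**What to change.** In SAP 10.2, define follow-up TEAEs as TEAEs with onset after the date of the last double-blind dose, in every subject who does not start LTSE drug, including those who terminate early. The smallest acceptable change is to anchor on the Week 24 or EOT visit. The last dose is the better anchor because the EOT visit may fall some days after it, and events in that interval would otherwise be missed.

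Add a sentence stating that follow-up TEAEs also remain in the overall TEAE tables. Add the table to Appendix A, by system organ class and preferred term and by preferred term alone, and flag these events in the adverse event listing.

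The cost is two sentences, the table shells and a listing flag. SAP 10.1.1 already uses the last-dose date for exposure, so no new data are needed. The change should be made before the double-blind database is locked. It affects an analysis definition only and no clinical rule.
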